11.13 Retention of Data

Essential documents should be retained until at least 2 years after the last approval of a marketing application and until there are no pending or contemplated marketing applications or

at least 2 years have elapsed since the formal discontinuation of clinical development of the investigational product. The sponsor will notify the investigator if these documents must be retained for a longer period of time. It is the responsibility of the sponsor to inform the Investigator or institution as to when these documents no longer need to be retained.

11.14 Financial Disclosure

The investigator should disclose any financial interests in the sponsor as described in 21 CFR Part 54 prior to beginning this study. The appropriate form will be provided to the investigator by the sponsor, which will be signed and dated by the investigator prior to the start of the study. Changes in status concerning financial interests during the study and for 1 year after its completion must be disclosed by the Investigator in accordance with 21 CFR Part 54.

11.15 Publication and Disclosure Policy

All information concerning the study material, such as patent applications, manufacturing processes, basic scientific data, and formulation information supplied by the sponsor and not previously published are considered confidential and will remain the sole property of the sponsor. The investigator agrees to use this information only in accomplishing this study and will not use it for other purposes.

It is understood by the investigator that the information developed in the clinical study may be disclosed as required to the authorized regulatory authorities and governmental agencies. In order to allow for the use of the information derived from the clinical studies, it is understood that there is an obligation to provide the sponsor with complete test results and all data developed in the study in a timely manner.

The investigator and any other clinical personnel associated with this study will not publish the results of the study, in whole or in part, at any time, unless they have consulted with Shire, provided Shire a copy of the draft document intended for publication, and obtained the written consent of Shire for such publication. All information obtained during the conduct of this study will be regarded as confidential. Shire will use the information for registration purposes and for the general development of the drug.

Appendix 1 Study Schedule of Events (No Attack)

(Pubertal/postpubertal subjects only)	Screening Period	Pre-treatment (Baseline)	Treatment	Post Treatment											Follow-up				
				Day 1											Day 2	Day 3	Day 8 (±1)	Day 90 (±7)	Month 6 (±7 days) Telephone Contact
Study Day		Day 1	Day 1	Day 1											Day 2	Day 3	Day 8 (±1)	Day 90 (±7)	
Time Post Treatment (hours)			0	0.25	0.5	0.75	1	2	4	6	8	24	48						
Window (hours or minutes)				(±5) min	(±5) min	(±5) min	(±10) min	(±10) min	(±0.5) hr	(±0.5) hr	(±0.5) hr	(±4) hr	(±4) hr						
Assessments																			
Informed Consent/Assent	X																		
Medical History	X	X																	
Documentation of HAE Attack(s) Not Treated with icatibant	X ^f															X			
Documentation of Pubertal Changes/Milestones																	X		
Confirm Documented HAE Diagnosis (via Sponsor's central lab)	X																		
C1-INH Assessment	X																		
Inclusion/Exclusion Assessment	X	X ^a																	
Physical Examination	X	X								X	X ^e			X	X				
Pubertal Status Determination ^b	X	X																	

(Pubertal/postpubertal subjects only)	Screening Period	Pre-treatment (Baseline)	Treatment	Post Treatment										Follow-up		
				Day 1										Day 2	Day 3	Day 8 (±1)
Study Day		Day 1	Day 1	0.25	0.5	0.75	1	2	4	6	8	24	48			
Time Post Treatment (hours)			0	(±5) min	(±5) min	(±5) min	(±10) min	(±10) min	(±0.5) hr	(±0.5) hr	(±0.5) hr	(±4) hr	(±4) hr			
Window (hours or minutes)																
Assessments																
Menstrual Cycle History (in pubertal/postpubertal females)		X													X	
Vital Signs	X	X					X			X	X ^c			X	X	
ECG	X									X	X ^c					
Height and Weight	X	X													X	
Clinical Laboratory Tests (serum chemistry, hematology, urinalysis)		X								X				X	X	
Urine Pregnancy Test (in females of childbearing potential)	X	X													X	
Reproductive Hormone Assessments (FSH, LH, estradiol, progesterone in females; FSH, LH, testosterone in males)		X								X				X	X	

(Pubertal/postpubertal subjects only)	Screening Period	Pre-treatment (Baseline)	Treatment	Post Treatment											Follow-up	
				Day 1											Day 2	Day 3
Study Day		Day 1	Day 1	0.25	0.5	0.75	1	2	4	6	8	24	48			
Time Post Treatment (hours)			0	(±5) min	(±5) min	(±5) min	(±10) min	(±10) min	(±0.5) hr	(±0.5) hr	(±0.5) hr	(±4) hr	(±4) hr			
Window (hours or minutes)																
Assessments																
Investigational Product Administration (single SC dose)			X													
Safety Follow-up Contact												X ^c	X ^c			
Injection Site Reaction Evaluation							X			X	X ^e	X ^c	X ^c	X		
PK Sampling ^d		X		X	X	X	X	X	X	X						
Immunogenicity Evaluation		X												X	X	
Concomitant Medications	X	X	X	X	X	X	X	X	X	X	X ^e	X ^c	X ^c	X	X	
Adverse Events			X	X	X	X	X	X	X	X	X ^e	X ^c	X ^c	X	X	

(Pubertal/postpubertal subjects only)	Screening Period	Pre-treatment (Baseline)	Treatment	Post Treatment										Follow-up				
				Day 1										Day 2	Day 3	Day 8 (±1)	Day 90 (±7)	Month 6 (±7 days) Telephone Contact
Study Day		Day 1	Day 1															
Time Post Treatment (hours)			0	0.25	0.5	0.75	1	2	4	6	8	24	48					
Window (hours or minutes)				(±5) min	(±5) min	(±5) min	(±10) min	(±10) min	(±0.5) hr	(±0.5) hr	(±0.5) hr	(±4) hr	(±4) hr					
Assessments																		

Abbreviations: FLACC = Faces, Legs, Activity, Cry, and Consolability (comportmental pain scale); FPS-R = Faces Pain Scale-Revised; FSH = follicle stimulating hormone; HAE = hereditary angioedema; hr = hour; LH = luteinizing hormone min = minute; PK = pharmacokinetic; SC = subcutaneous

- ^a The inclusion/exclusion criteria will be confirmed at the Pretreatment (Baseline) Visit.
- ^b A subject’s classification as prepubertal or pubertal/postpubertal will be determined at the Day 1 pretreatment visit. Note that a subject classified as pubertal/postpubertal at screening will not require further evaluation of pubertal status during the study.
- ^c These assessments may be conducted by telephone contact.
- ^d The PK sampling times shown are for pubertal/postpubertal subjects.
- ^e A subject may be discharged after completion of all assessments at 6 hours post treatment, if deemed medically stable in the investigator’s clinical judgment. If this is the case, the assessments scheduled for 8 hours post treatment will be omitted.
- ^f For all subjects who remain enrolled in the study for longer than 6 months, a telephone contact will be scheduled every 6 months to collect information concerning HAE attacks not treated with icatibant in the study.

Appendix 2 Study Schedule of Events (Initial Icatibant-treated Attack)

Initial Icatibant-treated Attack (All Subjects)	Screening Period	Pre-treatment (Baseline)	Treatment	Post Treatment											Follow-up				
				Day 1											Day 2	Day 3	Day 8 (±1)	Day 90 (±7)	Month 6 (±7 days) Telephone Contact
Study Day		Day 1	Day 1	Day 1											Day 2	Day 3	Day 8 (±1)	Day 90 (±7)	
Time Post Treatment (hours)			0	0.25	0.5	0.75	1	2	4	6	8 ^e	24	48						
Window (hours or minutes)				(±5) min	(±5) min	(±5) min	(±10) min	(±10) min	(±0.5) hr	(±0.5) hr	(±0.5) hr	(±4) hr	(±4) hr						
Assessments																			
Informed Consent/Assent	X																		
Medical History	X	X																	
Documentation of HAE Attack(s) Not Treated with icatibant	X ^h															X			
Documentation of Pubertal Changes/Milestones																	X		
Confirm Documented HAE Diagnosis (via Sponsor's Central Laboratory)	X																		
C1-INH Assessment	X																		
Inclusion/Exclusion Assessment	X	X ^a																	
Physical Examination	X	X								X ^g	X ^g			X	X				

Initial Icatibant-treated Attack (All Subjects)	Screening Period	Pre-treatment (Baseline)	Treatment	Post Treatment											Follow-up		
				Day 1									Day 2	Day 3	Day 8 (±1)	Day 90 (±7)	Month 6 (±7 days) Telephone Contact
Study Day		Day 1	Day 1	Day 1									Day 2	Day 3	Day 8 (±1)	Day 90 (±7)	
Time Post Treatment (hours)			0	0.25	0.5	0.75	1	2	4	6	8 ^e	24	48				
Window (hours or minutes)				(±5) min	(±5) min	(±5) min	(±10) min	(±10) min	(±0.5) hr	(±0.5) hr	(±0.5) hr	(±4) hr	(±4) hr				
Assessments																	
Pubertal Status Determination ^b	X	X															
Menstrual Cycle History (in pubertal/postpubertal females)		X													X		
Vital Signs	X	X					X			X ^g	X ^g			X	X		
ECG	X									X ^g	X ^g						
Height and Weight	X	X													X		
Subject Self-assessment of HAE-related Pain Using diary FPS-R (in subjects 4 years of age and older, and before blood work, if applicable)		X					X	X	X	X ^f	X ^{e,f}	X	X				
Investigator Assessment of HAE Symptoms		X					X	X	X	X ^f	X ^f						

Initial Icatibant-treated Attack (All Subjects)	Screening Period	Pre-treatment (Baseline)	Treatment	Post Treatment											Follow-up		
				Day 1									Day 2	Day 3	Day 8 (±1)	Day 90 (±7)	Month 6 (±7 days) Telephone Contact
Study Day		Day 1	Day 1	Day 1									Day 2	Day 3	Day 8 (±1)	Day 90 (±7)	
Time Post Treatment (hours)			0	0.25	0.5	0.75	1	2	4	6	8 ^e	24	48				
Window (hours or minutes)				(±5) min	(±5) min	(±5) min	(±10) min	(±10) min	(±0.5) hr	(±0.5) hr	(±0.5) hr	(±4) hr	(±4) hr				
Assessments																	
Investigator Assessment of HAE-related Pain Using FLACC (in subjects younger than 4 years of age, and before blood work, if applicable)		X					X	X	X	X ^f	X ^f						
Clinical Laboratory Tests (serum chemistry, hematology, urinalysis)		X								X				X	X		
Urine Pregnancy Test (in females of childbearing potential)	X	X													X		
Reproductive Hormone Assessments (FSH, LH, estradiol, progesterone in females; FSH, LH, testosterone in males)		X								X				X	X		

Initial Icatibant-treated Attack (All Subjects)	Screening Period	Pre-treatment (Baseline)	Treatment	Post Treatment											Follow-up		
				Day 1									Day 2	Day 3	Day 8 (±1)	Day 90 (±7)	Month 6 (±7 days) Telephone Contact
Study Day		Day 1	Day 1	Day 1									Day 2	Day 3	Day 8 (±1)	Day 90 (±7)	
Time Post Treatment (hours)			0	0.25	0.5	0.75	1	2	4	6	8^e	24	48				
Window (hours or minutes)				(±5) min	(±5) min	(±5) min	(±10) min	(±10) min	(±0.5) hr	(±0.5) hr	(±0.5) hr	(±4) hr	(±4) hr				
Assessments																	
Investigational Product Administration (single SC dose)			X														
Safety Follow-up Contact												X ^c	X ^c				
Injection Site Reaction Evaluation							X			X ^f	X ^f	X ^c	X ^c	X			
PK Sampling ^d		X		X	X	X	X	X	X	X							
Immunogenicity Evaluation		X												X	X		
Concomitant Medications	X	X	X	X	X	X	X	X	X	X ^f	X ^f	X ^c	X ^c	X	X		
Adverse Events			X	X	X	X	X	X	X	X ^f	X ^f	X ^c	X ^c	X	X		

Initial Icatibant-treated Attack (All Subjects)	Screening Period	Pre-treatment (Baseline)	Treatment	Post Treatment										Follow-up		
														Month 6 (±7 days) Telephone Contact		
Study Day		Day 1	Day 1	Day 1								Day 2	Day 3	Day 8 (±1)	Day 90 (±7)	
Time Post Treatment (hours)			0	0.25	0.5	0.75	1	2	4	6	8 ^e	24	48			
Window (hours or minutes)				(±5) min	(±5) min	(±5) min	(±10) min	(±10) min	(±0.5) hr	(±0.5) hr	(±0.5) hr	(±4) hr	(±4) hr			
Assessments																

Abbreviations: FLACC = Faces, Legs, Activity, Cry, and Consolability (comportmental pain scale); FPS-R = Faces Pain Scale-Revised; FSH = follicle stimulating hormone; HAE = hereditary angioedema; hr = hour; LH = luteinizing hormone min = minute; PK = pharmacokinetic; SC = subcutaneous

- ^a The inclusion/exclusion criteria will be confirmed at the Pretreatment (Baseline) Visit.
- ^b A subject’s classification as prepubertal or pubertal/postpubertal will be determined at the Day 1 pretreatment visit. Note that a subject classified as pubertal/postpubertal at screening will not require further evaluation of pubertal status during the study.
- ^c These assessments may be conducted by telephone contact.
- ^d The PK sampling times shown are for pubertal/postpubertal subjects. Prepubertal subjects will have blood samples drawn on Day 1 prior to dosing and at 15 (±5) minutes, 30 (±5) minutes, 2 hours (±10 minutes), 4 (±0.5) hours, and 6 (±0.5) hours post dose as indicated in Section 8.3.2.
- ^e A subject may be discharged after completion of all assessments at 6 hours post treatment, if deemed medically stable in the investigator’s clinical judgment and the subject’s HAE symptoms have resolved (the subject’s investigator-rated symptom score = zero, denoting the absence of symptoms). If this is the case, the assessments scheduled for 8 hours post treatment will be omitted with the exception of subject self-assessment of HAE-related pain using the diary FPS-R.
- ^f If the subject’s HAE symptoms have not resolved at 6 hours post treatment (the subject’s investigator-rated symptom score ≠ zero) and the subject is not to be discharged after completion of assessments at the 6-hour time point, the assessments indicated will be performed at both 6 AND 8 hours post treatment.
- ^g If the subject’s HAE symptoms have not resolved at 6 hours post treatment (the subject’s investigator-rated symptom score ≠ zero) and the subject is not to be discharged after completion of assessments at the 6-hour time point, the assessments indicated will be performed at either 6 OR 8 hours post treatment.
- ^h For all subjects who remain enrolled in the study for longer than 6 months, a telephone contact will be scheduled every 6 months to collect information concerning HAE attacks not treated with icatibant in the study.

Appendix 3 Study Schedule of Events (Subsequent Icatibant-treated Attacks)

	Subsequent Icatibant-Treated Attack Baseline ^a (Site)	Every Month after Baseline (Home) ^b	Treatment					Post Treatment		
			Day 1 (Site or Home)				Day 2 (Home)	Day 8 (±1) ^c (Site)	Day 90 (±7) ^c (Site)	
			Prior to Dosing	0	1	2	6-8	24		
Time Post Treatment (hours)										
Window (hours or minutes)				(±10) min	(±10) min	(±4) hr	(±4) hr			
Assessments										
Inclusion/Exclusion Assessment	X	X								
Menstrual Cycle History	X									X
Documentation of HAE Attack(s) Not Treated with icatibant	X	X								X
Physical Examination	X									X
Vital Signs	X								X	X
Height and Weight	X									X
Clinical Laboratory Tests (serum chemistry/hematology)	X									X
Urine Pregnancy Test (in females of childbearing potential)	X		X							X
Reproductive Hormone Assessments (FSH, LH, estradiol, progesterone in females; FSH, LH, testosterone in males)	X								X	X
Immunogenicity Evaluation	X								X	X
Training on icatibant administration ^d	X									
Training on how to assess HAE symptoms, time to initial symptom relief, and injection site reactions ^d	X									
Dispense 1 syringe of icatibant ^d	X									
Contact investigator with weight to confirm dose ^d		X								
Contact investigator in the event of an HAE attack			X ^b							
Investigational Product Administration (single SC dose)				X ^c						
Subject Self-assessment of HAE-related Pain Using FPS-R			X		X	X ^f	X ^f	X		
Investigator Assessment of HAE Symptoms			X ^g		X ^{g,h}	X ^{g,h}	X ^{g,h}			
Home Healthcare Provider or Parent/Legal Guardian/Caregiver Assessment of HAE Symptoms			X		X ^h	X ^h	X ^h			
Record Injection Site Reactions					X ^{b,i}	X ^{b,i}	X ^{b,i}	X ^c	X	
Safety Follow-up Contact							X ^b			
Concomitant Medications	X	X	X ^b	X ^b	X ^b	X ^b	X ^b	X ^b	X	X
Adverse Events	X	X	X ^b	X ^b	X ^b	X ^b	X ^b	X ^b	X	X

	Subsequent Icatibant-Treated Attack Baseline ^a (Site)	Every Month after Baseline (Home) ^b	Treatment						Post Treatment	
			Day 1 (Site or Home)				Day 2 (Home)	Day 8 (±1) ^c (Site)	Day 90 (±7) ^c (Site)	
Time Post Treatment (hours)			Prior to Dosing	0	1	2	6-8	24		
Window (hours or minutes)					(±10) min	(±10) min	(±4) hr	(±4) hr		
Assessments										
Return study drug ^d									X	

Abbreviations: FPS-R=Faces Pain Scale-Revised; FSH=follicle stimulating hormone; HAE=hereditary angioedema; LH=luteinizing hormone; SC = subcutaneous

^a All evaluations and sample collections must be performed at the hospital/study center within 6 months prior to treatment if a repeat attack does not occur within 6 months. If a second “baseline” visit is conducted due to lack of repeat attacks, one of the monthly phone calls may overlap with the onsite visit. In this case, a monthly call would not be necessary.

^b These assessments may be conducted by telephone contact.

^c If a subsequent attack occurs within 3 days of the Day 8 follow-up visit for the previous attack, the visits for Day 1 (of the subsequent icatibant-treated attack) and Day 8 (of the prior icatibant-treated attack) will be combined. If a subsequent attack occurs within 7 days of the Day 90 follow-up visit for the previous attack, the visits for Day 8 (of the subsequent icatibant-treated attack) and Day 90 (of the prior icatibant-treated attack) will be combined.

^d For subjects who have expressed an interest in self-administering or having a parent/legal guardian/caregiver administer icatibant in the home.

^e For subsequent attacks, study drug may be administered by study site personnel at the hospital/study center or by qualified home healthcare personnel at the subject’s home. Alternatively, a parent/legal guardian/caregiver will be allowed to administer or the subject (under the supervision of a parent/legal guardian/caregiver) will be allowed to self-administer the investigational product after having received appropriate training. For all subsequent laryngeal attacks, subjects should be advised to seek medical attention in an appropriate healthcare facility immediately following treatment with icatibant.

^f If after the completion of the assessments scheduled for 2 hours post-treatment, the subject’s pain is absent, no further Day 1 assessments are required. If the subject’s pain at 2 hours post-treatment is NOT absent, the subject will be assessed every 2 hours until pain is absent.

^g For subjects treated at the hospital/study center only.

^h The subject will be observed for a minimum of 2 hours after icatibant administration. If after the completion of the assessments scheduled for 2 hours post-treatment, the subject’s symptoms are absent or mild, no further Day 1 assessments are required. If the subject’s symptoms at 2 hours post-treatment are moderate, severe, or very severe, the subject will be assessed every 2 hours until the subject’s symptoms are absent or mild.

ⁱ Injection site reaction will be recorded (1 hour [±10 minutes] post dose and 2 [±0.5] hours post dose, and every 2 [±0.5] hours until injection site reaction is mild or absent (if the subject’s injection site reaction is not mild or absent at 2 hours post dose)

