3.2 Secondary Endpoints

Secondary endpoints (only for subjects treated with icatibant during a HAE attack):

- Time to onset of relief of symptoms and time to minimal symptoms, as measured by investigator- and subject-reported outcomes.
 - For all subjects (2 to <18 years of age): investigator assessment and scoring of cutaneous, abdominal, and laryngeal symptoms of acute HAE attacks by an investigator-rated symptom score.
 - The time to onset of relief of symptoms, defined as the earliest time at which at least a 20% improvement is seen in the average post-treatment score with no worsening of any single component score.
 - The time to minimal symptoms, defined as the earliest time post treatment when all symptoms are either mild or absent based on the investigator-rated symptom score.
 - For subjects ≥ 4 years of age only: subject self-assessment of HAE-related pain using the Faces Pain Scale-Revised (FPS-R).
 - The time to onset of relief of symptoms, defined as the earliest time at which the post-treatment score improves by at least one level.
 - The time to minimal symptoms, defined as the earliest time at which the post-treatment score improves to zero (or no pain).
 - For subjects <4 years of age only: investigator assessment of HAE-related pain (cutaneous, abdominal, and laryngeal) using a validated pain scale (Faces, Legs, Activity, Cry, and Consolability [FLACC]).
 - The time to onset of relief of symptoms, defined as the earliest time at which a 20% improvement is seen in the total post-treatment score.
 - The time to minimal symptoms, defined as the earliest time at which the total post-treatment score improves to zero.
- Incidence of rescue medication use.
- Proportion of subjects with worsened intensity of clinical HAE symptoms between 2 and 4 hours after treatment with icatibant.

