4.1.3.2 Subsequent Icatibant-Treated Attacks

Subsequent treatment with icatibant may be offered to pubertal/postpubertal subjects who have received initial treatment and who present subsequently with an attack at least 3 days after prior treatment. Subjects will be eligible for treatment with icatibant until a total number of at least 10 adolescents have been treated 3 times with icatibant.

For all subjects who remain enrolled in the study for longer than 6 months, a study visit will be scheduled every 6 months to collect baseline information and to conduct training for parents/legal guardian/caretakers for subjects who have expressed an interest in receiving icatibant at home. In addition, for all subjects who remain enrolled in the study a safety telephone contact will be scheduled every month to collect information concerning AEs, weight, eligibility, and HAE attacks not treated within the study.

When a pubertal/postpubertal subject experiences an acute HAE attack, subjects (parent/legal guardian/caregiver) will contact the hospital/study center (or their home healthcare professional in the event the investigator is not available) to confirm the HAE attack diagnosis.

The investigator (or the home healthcare professional in the event the investigator is not available), in consultation with the subject's preference, will determine whether the subject will be treated at the hospital/study center, at home by a qualified home healthcare personnel, or at home by the trained parent/legal guardian/caregiver. The qualified home healthcare person will be contacted, if applicable.

For subsequent attacks, study drug may be administered by study site personnel at the hospital/study center or by qualified home healthcare personnel at the subject's home. Alternatively, a parent/legal guardian/caregiver will be allowed to administer or the subject (under the supervision of a parent/legal guardian/caregiver) will be allowed to self-administer the investigational product after having received appropriate training. For all subsequent laryngeal attacks, subjects should be advised to seek medical attention in an appropriate healthcare facility immediately following treatment with icatibant.

Except for PK determinations, all primary and secondary endpoints are to be measured after each administration. Safety, reproductive hormones, and other assessments in association with

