- Study drug may be administered by study site personnel at the hospital/study center or by qualified home healthcare personnel at the subject's home. Alternatively, a parent/legal guardian/caregiver will be allowed to administer or the subject (under the supervision of a parent/legal guardian/caregiver) will be allowed to self-administer the investigational product after having received appropriate training.
- For all subsequent laryngeal attacks, subjects should be advised to seek medical attention in an appropriate healthcare facility immediately following treatment with icatibant.

The subject will be observed by the investigator, the home healthcare provider or the parent/guardian/caregiver for a minimum of 2 hours after icatibant administration.

The following will occur after icatibant administration:

	Subject Treated at Study Site	Subject Treated at Home
Icatibant Administration	X	X
Investigator Symptom Score	X	
Home Healthcare Provide or Parent/Legal Guardian/Caregiver Symptom Score	X	X
Subject Self-Assessment of Pain	X	X
Injection site reaction evaluation	X	X
Concomitant Medications	X	X
Adverse Events	X	X
Contact site 6 to 8 hours after attack	X	X

- HAE symptoms will be assessed at Day 1, 1 hour [± 10 minutes] post dose and 2 hours [± 10 minutes] post dose AND every 2 hours [± 10 minutes] until the subject's symptoms are absent or mild [if the subject's symptoms are not absent or mild at 2 hours post dose]
 - The investigator will assess HAE symptoms using the Investigator Symptom Score and record the time of initial symptom relief if the subject is treated at the hospital/study center
 - The home healthcare provider will assess HAE symptoms using the Home Healthcare Provider or Parent/Legal Guardian/Caregiver Symptom Score and record the time of initial symptom relief if the subject is treated at home
 - The parent/legal guardian/caregiver will assess HAE symptoms using the Home Healthcare Provider or Parent/Legal Guardian/Caregiver Symptom Score if the subject is treated at either the hospital/study site or at home
- The subject will self-assess pain using diary FPS-R (1 hour [± 10 minutes] post dose and 2 hours [± 10 minutes] post dose, and every 2 hours [± 10 minutes] until pain is absent [if the subject's pain is not absent at 2 hours post dose]);

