10.7 Efficacy Analyses

Efficacy analyses will be performed on the Efficacy Population. The primary efficacy endpoint is the time to onset of symptom relief measured using the investigator-reported symptom score. For the initial icatibant-treated attack, the investigator will report symptom scores at pretreatment and 1, 2, 4, and 6 hours post treatment, and at 8 hours post treatment for subjects who had not shown complete resolution of HAE symptoms at 6 hours. For subsequent icatibant-treated attacks, the investigator will report symptom scores at pretreatment and 1 and 2 hours post treatment, and every 2 hours afterwards until discharge. Eight symptoms will be assessed for abdominal and cutaneous attacks, and 13 symptoms will be assessed for laryngeal attacks. Time to onset of symptom relief is defined as the earliest time post treatment at which there is a 20% improvement in the average post-treatment symptom score with no worsening of any single component score. The median time and the 95% confidence interval will be calculated using the Kaplan-Meier methodology.

A tabular summary of the average investigator-reported symptom score and the change from baseline in the average investigator-reported symptom score will be presented by the stratification group and the icatibant exposure number. An alternative analysis will focus on the time to minimal symptoms and is defined as the time from study drug administration to the earliest time post treatment when all symptoms are either absent or mild. The median time and 95% confidence interval will be calculated using Kaplan-Meier methodology.

For individual investigator-reported symptom scores, a shift table from baseline will be presented for each post-treatment time point. The analysis will be repeated to assess shift in the individual symptom scores from the 2 hour time-point. Also, for individual symptoms that are moderate or worse at pretreatment, the median and 95% confidence interval will be presented for the time to the symptom being mild or absent.

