g For subjects treated at the hospital/study center only.

- h The subject will be observed for a minimum of 2 hours after icatibant administration. If after the completion of the assessments scheduled for 2 hours post-treatment, the subject's symptoms are absent or mild, no further Day 1 assessments are required. If the subject's symptoms at 2 hours post-treatment are moderate, severe, or very severe, the subject will be assessed every 2 hours until the subject's symptoms are absent or mild.
- i Injection site reaction will be recorded (1 hour [ $\pm 10$  minutes] post dose and 2 [ $\pm 0.5$ ] hours post dose, and every 2 [ $\pm 0.5$ ] hours until injection site reaction is mild or absent (if the subject's injection site reaction is not mild or absent at 2 hours post dose)

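### In subsequent attacks a 4-hour symptom score is required only if symptoms are still moderate or worse at 2 hours, although 2-to-4-hour worsening is to be measured after every administration

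*Protocol*

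**What the plan says.** **The endpoint and its scope.** Protocol 3.2 lists as a secondary endpoint: "Proportion of subjects with worsened intensity of clinical HAE symptoms between 2 and 4 hours after treatment with icatibant". SAP 5 lists it too. Protocol 4.1.3.2 says of subsequent attacks: "Except for PK determinations, all primary and secondary endpoints are to be measured after each administration". Protocol 4.1.2 says the same. SAP 7.8.1 defines no proportion for this endpoint. Its only analysis of change from 2 hours is a shift table of individual investigator scores, and Table 14.2.4.8 extends that to exposures 2 and 3.

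**The first attack.** Protocol 10.7 fixes the times for every subject: "the investigator will report symptom scores at pretreatment and 1, 2, 4, and 6 hours post treatment".

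**Subsequent attacks.** Protocol 8.4.2.1 sets scores at 1 and 2 hours. Scoring then continues two-hourly only if the subject's "symptoms are not absent or mild at 2 hours post dose". Footnote h of Protocol Appendix 3 gives the other side of the rule: if the subject's "symptoms are absent or mild, no further Day 1 assessments are required". SAP 10.3.3 repeats it: if the subject's "symptoms at 2 hours post-treatment are moderate, severe, or very severe, the subject will be assessed every 2 hours". In both schedule tables the row "Investigator Assessment of HAE Symptoms" has post-dose entries at 1, 2 and 6-8 hours. There is no 4-hour column, and those entries carry footnote h.

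**A different wording.** For subsequent attacks, Protocol 10.7 has the investigator score at pretreatment and "1 and 2 hours post treatment, and every 2 hours afterwards until discharge".

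**The concern.** The endpoint asks whether symptoms get worse again after the first two hours. For that question the informative attacks include those that had already settled by 2 hours, because a return of symptoms there is a worsening. Those are the attacks in which the subsequent-attack schedule lets scoring stop. Whether the 4-hour score exists thus depends on the outcome at 2 hours, so following the plan exactly produces informative gaps.

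At stake is what can be said about exposures 2 and 3. A low or zero worsening figure could be read as durable response when durability was not measured in the early responders. It would also not be comparable with the first-attack figure, where the 4-hour score is fixed for all.

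**Working it through.** **Step 1: does anything in the plan secure a 4-hour score?**

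- *Investigator score.* Under Protocol 8.4.2.1 and both footnotes h, only if symptoms are moderate or worse at 2 hours. Footnote g limits it further to subjects treated at the hospital or study center.
- *Protocol 10.7, two-hourly until discharge.* Required observation in subsequent attacks is only 2 hours (8.4.2.1), no discharge time is set, and home-treated subjects have no discharge. This may yield some 4-hour scores at site but guarantees none.
- *Caregiver or home healthcare score.* It carries the same footnote h. Protocol 10.7 plans its shifts from baseline only, and SAP 7.8 does not name it among the efficacy data.
- *FPS-R.* Two-hourly until pain is absent, so some subjects have a 4-hour pain score. It is not a symptom score.
- *Contact at 6 to 8 hours.* An update on the subject's condition, not a scheduled 4-hour score.
- *CRF record of clinically relevant worsening (Protocol 7.17.1.1).* No section assigns it to this endpoint, and no listed SAP output summarises it.

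**Step 2: how common might the gap be?** The documents do not say. Protocol 1.2.2 reports, for the initial treatment, a median time to minimal symptoms of 1.0 hour (95% CI 1.0 to 2.0) in pubertal/postpubertal subjects. Minimal means every symptom mild or absent, which is also the condition for stopping at 2 hours. If repeat attacks behave alike and early relief holds to 2 hours (both assumptions), about half or more could stop. SAP 7.8.1 excludes from that median subjects already mild or absent before treatment, who would also tend to meet the stop condition.

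**Step 3: effect on the result.** Take n attacks, u without a 4-hour score, and w seen to worsen among the n − u scored. The true share lies between w/n and (w + u)/n. For illustration n = 10, because Protocol 4.1.3.2 aims for at least 10 adolescents treated three times. With w = 0:

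| u (assumed) | Reported | Largest possible true share |
|---|---|---|
| 3 | 0% | 3/10 = 30% |
| 5 | 0% | 5/10 = 50% |
| 8 | 0% | 8/10 = 80% |

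The reported figure is 0% whether unscored attacks are left out or counted as not worsened. The last column is a logical limit, reached only if every unscored attack worsened. It is not an estimate.

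Precision suffers as well. With no worsening in m scored attacks, the exact upper 97.5% limit is 1 − 0.025^(1/m): 52% for m = 5 and 31% for m = 10. With m = 5 it would describe only attacks still moderate or worse at 2 hours.

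**Step 4: what happens to an absent score?** Protocol 10.10 has a general last-observation-carried-forward sentence. If it applies, the 2-hour value becomes the 4-hour value and the attack counts as not worsened. SAP 9.2.1 carries forward only single items missing within an assessment that took place, and is silent on an assessment that was never done.

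**Step 5: which attacks fall under this schedule?** Some subjects receive their first dose without an attack, so their first treated attack is exposure 2. Table 4-1 and Appendix 2 assign the initial treated attack, for all subjects, to the full schedule with a fixed 4-hour score. Protocol 4.1.2 and 8.4 can be read as treating any attack after an initial treatment as subsequent. The documents do not settle it.

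**The case against.** The best case for the plan is that the shorter schedule is a sensible response to home treatment and that worsening is caught in other ways. The endpoint names no instrument or rater, unlike the time-to-relief endpoints beside it. Clinically relevant worsening goes on a CRF page, pain scoring continues while pain lasts, a contact is due at 6 to 8 hours, and Protocol 10.7 may add site scores. This stands as partial cover. It does not remove the gap, because none of these is a scheduled 4-hour symptom score and the only planned analysis of change from 2 hours uses investigator symptom scores.

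Three stronger readings are tempting and should be resisted:

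- A reader might infer that every exposure-2 and exposure-3 attack falls under the stop rule. The ambiguity in step 5 means that some exposure-2 attacks may already have a fixed 4-hour score.
- A reader might infer that protocol and SAP impose two competing denominators, each giving its own percentage. SAP 9.2.1 states no rule for a whole missing assessment, whether a score never required counts as missing under Protocol 10.10 is itself open, and Protocol 10.1 leaves non-PK methods to the SAP. What the documents support is that the handling is unclear.
- A reader might take 10 as the denominator of Table 14.2.4.8. That table is investigator-only, and home-treated attacks have no investigator score, so its counts could be smaller.

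It is also fair that repeat-exposure efficacy is one of the other objectives (Protocol 2.2), is descriptive, and involves no formal test.

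**Conclusion.** The point holds for attacks followed under the subsequent-attack schedule. The plan commits to measuring 2-to-4-hour worsening after each administration, but its schedule does not require the second measurement in attacks that are absent or mild at 2 hours. The missing scores depend on outcome, and their handling is not settled.

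The size cannot be fixed from the documents. With 5 of 10 attacks unscored and none seen to worsen, 0% would be reported while up to 50% could have worsened; for 3 or 8 unscored the limit is 30% or 80%. The unscored counts are assumptions, and the middle case assumes that repeat attacks resemble first attacks. Confidence is high in the textual conflict and low in any particular magnitude. The consequence is limited to the claims made for exposures 2 and 3: the change should be made, but it does not threaten the first-attack results.

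**What to change.** **If data are still being collected.** Schedule one 4-hour symptom score in every subsequent attack, whatever the 2-hour score, by the rater already scoring: the investigator if the subject is still at site, otherwise the home healthcare provider or a trained caregiver. Rating training is now scheduled only for families interested in home or self-administration (Protocol 8.4.1; Appendix 3, footnote d), so extend it to caregivers of site-treated subjects. Tabulate shifts from 2 hours by rater. Reconcile Protocol 10.7 with 8.4.2.1 and Appendix 3, and state which schedule covers a first treated attack that is exposure 2.

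**If collection is closed.** In Table 14.2.4.8 use as denominator only attacks with an observed 4-hour score, split by 2-hour severity, and carry no 2-hour score forward. SAP 8.2 now reports no change from the protocol's analyses. Amend it to say that 2-to-4-hour worsening was not fully measured in attacks under the subsequent-attack schedule.

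**Cost.** One extra score per subsequent attack, wider use of existing training, and a caregiver-rated shift table. After closure, the cost is a narrower stated endpoint for those attacks, recorded as a departure from Protocol 4.1.3.2.
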